4.15 Protocol Violations

A list of major protocol violations that could potentially impact the analysis of the study will be determined during the conduct of the study by study team members who are blinded to study treatment being received. These will be presented in a listing.

4.16 Interim Analyses and Data Monitoring

An independent DMC will review unblinded safety data on an ongoing basis (Protocol Section 9.4.5). These will consist of the following:

- Listing of individual SAEs
- Table of SAEs by treatment group
- Table of TEAEs by treatment group
- Table of NIAID ordinal scale assessment – worst value per patient by treatment group
- Table of demographics by treatment group
- Table of Baseline disease characteristics by treatment group

If the DMC requests and the sponsor agrees to conducting a futility analysis, the conditional power for the primary efficacy analysis will be assessed via simulations, using the data collected so far to predict the remaining data to be collected.

Ongoing monitoring of safety data (including AEs, SAEs, and selected laboratory measurements) will continue throughout the study by the sponsor using blinded data.

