9.4.5. Safety Monitoring

The study will have a Data Monitoring Committee (DMC) consisting of at least 2 physicians and one statistician, all experienced clinical trialists and external to the sponsor. The role of the DMC is to advise the sponsor regarding conduct of the study. Only the DMC is authorized to evaluate unblinded data. Study sites will receive unblinded results ONLY if they need to know for the safety of their patients. Unblinding details are specified in the unblinding plan section of the statistical analysis plan (SAP) or a separate unblinding plan document.

In the event that safety monitoring uncovers an issue that needs to be addressed by unblinding at the group level, only members of the DMC can conduct additional analyses of the safety data.

All deaths and SAE reports will be reviewed in a blinded manner by Lilly during the clinical trial. These reports will be reviewed to assure completeness and accuracy but will not be unblinded to Lilly during the clinical trial. If a death or clinical AE is deemed serious, unexpected, and possibly related to investigational product, one individual (or designee) in Lilly Global Patient Safety will be unblinded for regulatory reporting and safety monitoring purposes. These measures will preserve the integrity of the data collected during this trial and minimize any potential for bias while providing for appropriate safety monitoring.

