4.13 Safety Analyses

All safety evaluations will be based upon the Safety Analysis Set.

Safety will be assessed by evaluating all reported AEs and changes in laboratory analytes, ECGs, and vital signs (including body weight) in the Safety Analysis Set and summarized by treatment group.

The baseline for computing the change in safety data is the last value collected before the first dose of study drug. The parameters will be listed and summarized with standard descriptive statistics. Change from baseline will also be summarized.

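### The DMC's listed safety package has no laboratory, ECG or vital-sign summary by arm, so on the supplied documents an imbalance in measured values not recorded as AEs would not be routinely visible during the trial.

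*SAP*

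**What the plan says.** SAP 4.16 (Interim Analyses and Data Monitoring) describes the DMC's package: "An independent DMC will review unblinded safety data on an ongoing basis (Protocol Section 9.4.5). These will consist of the following". Six items follow:

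1. a listing of individual SAEs;
2. "Table of SAEs by treatment group";
3. "Table of TEAEs by treatment group";
4. the NIAID ordinal scale, "worst value per patient by treatment group";
5. "Table of demographics by treatment group";
6. baseline disease characteristics by arm.

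The same section assigns the sponsor's role: "Ongoing monitoring of safety data (including AEs, SAEs, and selected laboratory measurements) will continue throughout the study by the sponsor using blinded data". Protocol 10.3.6 has the same provision and refers to a DMC Charter for the details of the DMC's review. Protocol 9.4.5 states: "Only the DMC is authorized to evaluate unblinded data".

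The safety assessment itself is wider. SAP 4.13 opens: "Safety will be assessed by evaluating all reported AEs and changes in laboratory analytes, ECGs, and vital signs (including body weight"), summarised by treatment group. Protocol 10.3.4 says the same. By-arm outputs for these domains are specified in SAP 4.13.3 to 4.13.5 and listed in SAP 5.1 as Tables 15-20 (hematology and chemistry) and 22-24 (vital signs and ECGs).

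**The concern.** The SAP's list is worded as what the package consists of, not as examples. Read as written, one of the four safety domains (adverse events) reaches the DMC by arm; laboratory values, ECGs and vital signs do not. The sponsor looks at selected laboratory measurements without knowing the arm, and ECGs and vital signs are not named in that provision.

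This matters because hospitalised patients with COVID-19 pneumonia can be expected to have abnormal values whatever they receive. A pooled abnormality rate cannot then be split into background and drug effect; only the comparison between arms can do that.

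Protocol 9.2.1 adds weight. It treats leukocytosis, leukopenia, tachycardia, bradycardia and temperature disturbance as clinical outcomes, not reported as SAEs unless the investigator attributes them to study drug. It relies on the DMC to watch for aggregate imbalance between the groups. These are laboratory and vital-sign phenomena, yet the DMC list has no laboratory or vital-sign table. Bleeding is also a reason to stop study drug (Protocol 8.1) and anticoagulation is permitted (Protocol 7.7), so hemoglobin and platelets by arm are of direct interest.

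**Working it through.** The main check is a comparison of texts; the plan has no figure to reproduce.

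**Step 1: safety domains against the DMC list.**

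| Domain (Protocol 10.3.4, SAP 4.13) | By arm in the SAP 4.16 list? | Planned by-arm output |
|---|---|---|
| Adverse events | Yes (items 1-3) | Tables 8-14 |
| Laboratory analytes | No | Tables 15-20 |
| Vital signs | No | Tables 22-23 |
| ECGs | No | Table 24 |

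Items 4 to 6 are the worst NIAID score and two baseline tables. SAP 4.16.1 adds ventilation status, discharge, mortality and ventilator-free days for the futility interim, on top of the regular safety package. It adds no laboratory, ECG or vital-sign output.

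**Step 2: does anyone else look by arm?**

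- Sponsor safety monitoring: blinded (SAP 4.16, Protocol 10.3.6).
- Global Patient Safety individual: unblinded for individual events and regulatory reporting (Protocol 7.3, 9.4.5).
- Sponsor assessment committee: for interim efficacy and futility (Protocol 10.3.6).
- Drug-preparation and laboratory staff: not blinded (Protocol 7.3), but given no comparative review task.

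None has a routine by-arm review of measured safety data.

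**Step 3: what by-arm tables would add.** The documents give no abnormality rates and no arm sizes at DMC reviews, so these counts are assumptions. They could stand, for example, for patients with a marked transaminase elevation. The test is Fisher's exact test.

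| Assumed split | Pooled rate | One-sided p | Two-sided p |
|---|---|---|---|
| 12/60 v 3/60 | 15/120 = 12.5% | 0.012 | 0.025 |
| 10/60 v 5/60 | 15/120 = 12.5% | 0.13 | 0.27 |
| 9/60 v 6/60 | 15/120 = 12.5% | 0.29 | 0.58 |
| 8/50 v 2/50 | 10/100 = 10% | 0.046 | 0.092 |
| 7/50 v 3/50 | 10/100 = 10% | 0.16 | 0.32 |

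The first three rows have the same pooled rate, so blinded review cannot tell them apart. By arm, the fourfold imbalances stand out (less clearly at 50 per arm), while a twofold imbalance or smaller does not reach conventional significance at these sizes. A DMC does not act on p-values alone, but the range shows that the gain is mainly in detecting large imbalances.

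**The case against.** The strongest objection is that the DMC Charter is not among the supplied documents. Protocol 10.3.6 names it as the place for details, directly after describing the DMC's ongoing safety review. It may already provide these tables. That stands: the documents show what the SAP list omits, not what the DMC actually received. If the Charter does provide them, the SAP list is incomplete and needs aligning.

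Second, two routes lead from measured values to the DMC. Under Protocol 9.4.1 to 9.4.3, clinically significant ECG, vital-sign and laboratory findings that lead to a diagnosis after the first dose are reported as AEs, and so can appear by arm in the TEAE table. Under Protocol 9.4.5, DMC members can run additional analyses once monitoring has uncovered an issue, and the sponsor's blinded laboratory review could prompt one. Both routes are real but partial. The first misses shifts and abnormal values that yield no diagnosis. The second is triggered by an issue, and the listed package would not itself show an imbalance in values that were never recorded as AEs.

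Third, the documents nowhere promise the DMC these tables. That is right: SAP 4.13 and Protocol 10.3.4 govern the study's safety analysis, not the DMC package, so this is a weakness in monitoring and not an internal contradiction.

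A reader might infer that nobody could see such data by arm, or that a laboratory or blood-pressure toxicity would be recognised only after final unblinding, when every patient had been dosed. The documents do not support either inference, given the possible Charter content, the by-arm SAE and TEAE tables, and the DMC's ad hoc analyses.

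**Conclusion.** The point holds in a limited form. The SAP's list for the DMC's ongoing unblinded review omits three of the four safety domains that the plan defines, and no other party is assigned a routine by-arm look at them. On the supplied documents, an imbalance in measured values not recorded as AEs would not be routinely visible while the trial runs.

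The conclusion rests on reading the SAP list as complete and on the Charter adding nothing, which cannot be checked. The size of the benefit depends on assumed rates: by-arm tables would flag a large imbalance (12/60 v 3/60, one-sided p = 0.012) but not clearly a mild one (10/60 v 5/60, p = 0.13). The primary analysis, type I error and power are unaffected. This is a cheap improvement to safety monitoring.

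**What to change.** Add to the SAP 4.16 list, by treatment group, for every DMC review still to come:

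- hematology and chemistry results, changes, shifts and abnormal values (Tables 15-20);
- vital signs and extreme vital signs (Tables 22-23);
- abnormal ECGs (Table 24).

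Run them on the DMC data cut, and make the SAP list and the DMC Charter agree. If the Charter already provides these outputs, bring the SAP list into line with it and cross-refer. SAP 4.16.1 describes the futility interim in the past tense, so the change can help only the reviews that remain.

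The cost is a short SAP edit and a run of table programs that are already planned. The downside is longer DMC reports and interim data that are not fully cleaned.

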4.16.1 Interim Analysis

After approximately 100 randomized patients have 28 day data available, an analysis was conducted to assess study futility. An unblinded snapshot of the eCRF database was used for this interim analysis. In addition to the safety data regularly provided to the DMC for their review, efficacy data consisting of ventilation status, hospital discharge, and mortality during days 1-28 as well as the calculation of ventilator free days (VFD) were provided for evaluation.

The conditional power for the primary efficacy analysis was calculated by the DMC Statistician, using the data collected as of the interim analysis to predict the data to be collected after the interim analysis. If this conditional power is less than 10%, then the DMC should recommend that the study be stopped: no new patients should be randomized, and no new doses of study drug given, but ongoing patients should be allowed to complete other protocol procedures and be followed to collect their full data.

4.17 Clinical Trial Registry Analyses

Additional analyses will be performed for the purpose of fulfilling the Clinical Trial Registry (CTR) requirements.

Analyses provided for the CTR requirements include the following:

Summary of adverse events, provided as a dataset which will be converted to an XML file. Both Serious Adverse Events and ‘Other’ Adverse Events are summarized: by treatment group, by MedDRA preferred term.

- An adverse event is considered ‘Serious’ whether or not it is a treatment emergent adverse event (TEAE).

- An adverse event is considered in the ‘Other’ category if it is both a TEAE and is not serious. For each Serious AE and ‘Other’ AE, for each term and treatment group, the following are provided:
 - The number of participants at risk of an event
 - The number of participants who experienced each event term
 - The number of events experienced.
- Consistent with www.ClinicalTrials.gov requirements, ‘Other’ AEs that occur in fewer than 5% of patients/subjects in every treatment group may not be included if a 5% threshold is chosen (5% is the minimum threshold).

AE reporting is consistent with other document disclosures for example, the CSR, manuscripts, and so forth.

5. List of TLFs

The numbering of the TLFs will be left for the medical writers to assign. The sequential numbers are provided below just for clarity. These numbers should be excluded from the TLFs.

5.1 List of Tables

	Title
1	Demographics and Baseline Characteristics (Safety Population)
2	Demographics and Baseline Characteristics by Site (Safety Population)
3	Analysis Populations
4	Patient Disposition by Treatment Group and Overall
5	Drug Exposure (Safety Population)
6	Concomitant Medications By Drug Class And Name (Safety Population)
7	Medical History (Safety Population)
8	Overview of Adverse Events (Safety Population)
9	Number and Percentage of Subjects with Treatment Emergent Adverse Events by System Organ Class and Preferred Term (Safety Population)
10	Number and Percentage of Subjects with Study Drug Related Treatment Emergent Adverse Events by System Organ Class and Preferred Term (Safety Population)
11	Number and Percentage of Subjects with Treatment Emergent Adverse Events by System Organ Class, Preferred Term, and Maximal Severity (Safety Population)
12	Serious Treatment Emergent Adverse Events by System Organ Class and Preferred Term (Safety Population)
13	Treatment Emergent Adverse Events Leading to Study Drug Discontinuation by System Organ Class and Preferred Term (Safety Population)
14	Treatment Emergent Adverse Events that Result in Death by System Organ Class and Preferred Term (Safety Population)
15	Hematology Lab Results by Study Day and Change from Baseline (Safety Population)
16	Chemistry Lab Results by Study Day and Change From Baseline (Safety Population)
17	Hematology Shift from Baseline (Safety Population)
18	Chemistry Labs Shift from Baseline (Safety Population)
19	Subjects with Abnormal Hematology Results (Safety Population)
20	Subjects with Abnormal Chemistry Results (Safety Population)
21	Pregnancy Status (Safety Population)
22	Vital Signs and Change from Baseline by Study Day (Safety Population)
23	Subjects with Extreme Vital Signs (Safety Population)

24	Number and Percentage of Subjects with Abnormal ECGs (Safety Population)
25	COVID-19, Influenza, RSV, and Respiratory Viral Panels (Safety Population)
26	(Primary Objective) Ventilator Free Days (Efficacy Population)
27	Ventilator Free Days by SARS-Cov-2 Status (Efficacy Population)
28	Ventilator Free Days by Age Group (Efficacy Population)
29	Ventilator Free Days by Sex (Efficacy Population)
30	Ventilator Free Days by BMI Group (Efficacy Population)
31	Ventilator Free Days by Number Of Doses (Efficacy Population)
32	Ventilator Free Days by NIAID = 2 within Day 4 (Efficacy Population)
33	Ventilator Free Days by NIAID = 3 vs. NIAID = 4 or 5 (Efficacy Population)
34	Ventilator Free Days by Remdesivir Use (Efficacy Population)
35	(Secondary Objective) Alive and Respiratory Failure Free Complete Response (Efficacy Population)
36	(Secondary Objective) NIAID Ordinal Assessments (Efficacy Population)
37	(Secondary Objective) Time to 2-Point Improvement on NIAID (Efficacy Population)
38	(Secondary Objective) Mortality Rate within 28 Days from Randomization (Efficacy Population)
39	(Secondary Objective) Mortality Rate within 60 Days from Randomization (Efficacy Population)
40	(Secondary Objective) Length of Hospitalization Stay (Efficacy Population)
41	(Secondary Objective) Hospital Discharge Rate at Day 28 (Efficacy Population)
42	(Other Objective) Pulmonary Function by Study Day (Efficacy Population)
43	(Other Objective) Supportive Pulmonary Care (Efficacy Population)

5.2 List of Data Listings

	Title
1	Analysis Populations (including exclusion reason from efficacy population)
2	Protocol Deviations
3	Demographics and Baseline
4	Patient Disposition
5	Drug Exposure
6	Concomitant Medications by Drug Class and Name
7	Medical History

8	Adverse Events
9	Serious TEAEs
10	All Deaths
11	Related TEAEs
12	Hematology Lab Results
13	Abnormal Hematology Lab Results
14	Chemistry Lab Results
15	Abnormal Chemistry Lab Results
16	Pregnancy Test Results
17	Vital Signs
18	Extreme Vital Signs
19	ECGs
20	Abnormal ECGs
21	Physical Exams
22	COVID-19, Influenza, RSV, and Respiratory Viral Panels
23	Thyroid Panels
24	Ventilator Free Days
25	Mortality and Respiratory Failure Status
26	NIAID Ordinal Assessments
27	Pulmonary Function
28	Hospitalizations
29	Supportive Pulmonary Care

5.3 List of Figures

	Title
1	NIAID Mean Score over Time by Treatment Group
2	NIAID Category over Time by Treatment Group (Stacked Bar Plot)
3	NIAID Category over Time by Treatment Group (Stacked Bar Plot) where Categories 3-5 are Combined and 6-8 are Combined
4	Time to 2-Point Improvement on NIAID (Kaplan-Meier Plot)
5	Pulmonary Function over Time by Treatment Group
